Nivolumab has demonstrated efficacy in the treatment of metastatic squamous and non-squamous NSCLC. In the phase III CheckMate-017 trial, 272 patients with metastatic squamous NSCLC who had progressed during or after one prior platinum doublet-based chemotherapy regimen were randomized (1:1) to receive nivolumab (n=135; 3 mg/kg intravenous [IV] every 2 weeks) or docetaxel (n=137; 75 mg/m² IV every 3 weeks) in an open label study.³³ This study included patients regardless of their PD-1 status. Patients with autoimmune disease, symptomatic interstitial lung disease, or untreated brain metastasis were excluded. Patients with treated brain metastases were eligible if their neurological status had returned to baseline at least 2 weeks prior to enrollment and they were either off corticosteroids or on a stable or decreasing dose of <10 mg daily prednisone equivalents. Tumor assessments were conducted 9 weeks after randomization and every 6 weeks thereafter. The major efficacy outcome measure was OS. The median OS was 9.2 months (range: 7.3–13.3 months) and 6.0 months (range: 5.1–7.3 months) for nivolumab and docetaxel, respectively (P = 0.00025). The median patient age was 63 years (range: 39–85 years); 44% and 11% of patients were ≥ 65 and ≥ 75 years of age, respectively. The majority of patients were white (93%) and male (76%). Baseline Eastern Cooperative Oncology Group (ECOG) performance status was 0 in 24% of patients and 1 in 76% of patients. This trial demonstrated a statistically significant improvement in OS with nivolumab as compared with docetaxel at the prespecified interim analysis conducted when 199 events were observed (86% of the planned number of events for the final analysis). A single-arm, multinational, multicenter trial of nivolumab was conducted in patients with metastatic squamous NSCLC whose disease had progressed after receiving a platinum-based therapy and at least one additional systemic treatment regimen.²⁶ This study included patients regardless of their PD-1 status. Nivolumab (3 mg/kg) was administered intravenously over 60 minutes every 2 weeks. Patients with autoimmune disease, symptomatic interstitial lung disease, or untreated brain metastasis were excluded. Patients with treated brain metastases were eligible if their neurological status had returned to baseline at least 2 weeks prior to enrollment and they were either off corticosteroids or on a stable or decreasing dose of <10 mg daily prednisone equivalents. Tumor assessments were conducted 8 weeks after treatment start and every 6 weeks thereafter. The major efficacy outcome measure was confirmed ORR as measured by an independent review committee (IRC) using the Response Evaluation Criteria in Solid Tumors version 1.1 (RECIST 1.1). Additional outcome measures included DOR. A total of 117 patients received treatment with nivolumab. The median age was 65 years (range: 37–87 years); 50% of patients were ≥ 65 years of age and 14% of patients were ≥ 75 years of age. The majority of patients were male (73%) and white (85%). All patients received two or more prior systemic treatments; 35% received two, 44% received three, and 21% received four or more. At baseline, 6%, 94%, and 1.7% of patients had recurrent stage IIIb disease, stage IV disease, and brain metastases, respectively. Baseline ECOG performance status was 0 in 22% of patients and 1 in 78% of patients. Based on IRC review and with a minimum follow-up of at least 10 months on all patients, the confirmed ORR was 15% (17/117; 95% CI: 9–22), of which all were partial responses. The median time to onset of response was 3.3 months (range: 1.7–8.8 months). Thirteen of the 17 patients (76%) with a confirmed response had ongoing responses with durations ranging from 1.9+ to 11.5+ months; 10 of these 17 (59%) patients had durable responses of 6 months or longer.

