therapy (yes vs. no) and number of prior therapies (1 vs. 2). The trial excluded patients with autoimmune disease, medical conditions requiring systemic immunosuppression, symptomatic interstitial lung disease, or untreated brain metastasis. Patients with treated brain metastases were eligible if neurologically stable. The first tumor assessments were conducted 9 weeks after randomization and every 6 weeks thereafter. The median patient age was 62 years (range: 21–85 years), with 42% of patients \geq 65 years of age and 7% of patients \geq 75 years of age. The majority of patients were white (92%), male (55%), and former/current smokers (79%). Most patients were enrolled in Europe (46%), followed by the US/Canada (37%) and the rest of the world (17%). Baseline ECOG performance status was 0 in 31% of patients and 1 in 69% of patients. *ALK* rearrangement and *EGFR* mutation were present in 3.6% and 14% of patients, respectively, and 12% of patients had previously treated brain metastases. Prior therapy included platinum-doublet regimen (100%), and 40% of patients had received maintenance therapy as part of their first-line regimen. Histologic subtypes included adenocarcinoma (93%), large cell (2.4%), and bronchoalveolar (0.9%). The major efficacy outcome measure was OS. Nivolumab significantly improved median OS compared with docetaxel at the prespecified interim analysis conducted when 413 events were observed (93% of the planned number of events for final analysis; 12.2 months vs. 9.4 months; $P = 0.0015$). The median DoR was 17 and 6 months with nivolumab and docetaxel, respectively. Complete responses (CRs) and partial responses (PRs) were achieved in 4 (1.4%) and 52 (18%) patients in the nivolumab arm and 1 (0.3%) patient and 35 (12%) patients in the docetaxel arm. PFS was 2.3 and 4.2 months in the nivolumab and docetaxel arms, respectively. Based on the results of these trials, nivolumab has been approved for the treatment of metastatic squamous and non-squamous NSCLC with progression on or after platinum-based chemotherapy. Patients with *EGFR* mutation or *ALK* translocation should have disease progression on appropriate targeted therapy prior to receiving nivolumab.

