5.1 Description of study design

This is a phase II window of opportunity study evaluating the efficacy and toxicity of SBRT and in situ gene therapy followed by nivolumab in metastatic squamous and non-squamous NSCLC and metastatic uveal melanoma.

Figure 1: Study design

PHASE II WINDOW OF OPPORTUNITY TRIAL OF STEREOTACTIC-BODY RADIATION THERAPY AND IN SITU GENE THERAPY FOLLOWED BY NIVOLUMAB IN METASTATIC SQUAMOUS OR NON-SQUAMOUS NON-SMALL CELL LUNG CARCINOMA AND METASTATIC UVEAL MELANOMA.
ENSIIGN TRIAL

6. Treatment

ADV/HSV-tk (5×10^{11} viral particles) in a 2-mL total volume will be injected intratumorally on day 0 of the study. **Valacyclovir** will be orally administered at a dose of 2 g three times daily (t.i.d.) for 14 days. For patients with serum creatinine level between $1.6-2.0 \times$ ULN, valacyclovir dose will be reduced 50% (i.e., 1 g t.i.d.). Valacyclovir treatment will be administered 24 hours after the gene vector injection from day 1 to day 15 of the study.

SBRT of 30 gray (Gy; 6 Gy X 5 fractions) will be administered over 2 weeks from day 2 to day 14 of the study.

Nivolumab (480 mg) will be administered intravenously over 30 minutes every 4 weeks (± 1 day) starting on day 17 of the study and continuing until disease progression, unacceptable toxicity, or up to 12 months in patients without disease progression.

Immune-mediated complications of nivolumab will be defined as immunological reactions requiring the use of corticosteroids. Grade 2 or greater immune-mediated complications must be managed with 1 to 2 mg/kg/day prednisone equivalents, followed by corticosteroid taper. Permanently discontinue nivolumab for severe (Grade 3) or life-threatening (Grade 4) immune-mediated complications and withhold nivolumab until resolution of moderate (Grade 2) immune-mediated complications. Based on the severity of the event, consider restarting nivolumab after completion of corticosteroid taper.

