8.2 Exclusion criteria:

- Prior treatment with gene therapy.
- Any immunotherapy within 2 weeks of study treatment start (NSCLC cohort only).
- Prior treatment with immunotherapy (uveal melanoma cohort only)
- Patients with *EGFR* or *ALK* genomic tumor aberrations that have not received any FDA-approved therapy for these aberrations (NSCLC cohort only).
- Oxygen-dependent chronic obstructive pulmonary disease (NSCLC cohort only).
- Patients requiring oral prednisone for emphysema management (NSCLC cohort only).
- History of liver disease, such as cirrhosis or active/chronic hepatitis B or C.
- History of or current alcohol misuse/abuse within the past 12 months.
- Known gallbladder or bile duct disease (i.e., infection or cholecystitis) or acute or chronic pancreatitis.
- Major surgery within 4 weeks prior to study enrollment.
- Uncontrolled brain or leptomeningeal metastases or brain or leptomeningeal metastases requiring continued glucocorticoid treatment. Patients who have been treated at least 4 weeks prior to enrollment and have a CT or MRI scan of the brain showing no evidence of disease progression within 4 weeks of enrollment are eligible.
- Congestive heart failure: New York Heart Association class III or IV heart failure or unstable angina.
- History of syncope or family history of idiopathic sudden death.
- Sustained or clinically significant cardiac arrhythmias including sustained ventricular tachycardia, ventricular fibrillation, clinically significant bradycardia, advanced heart block (Mobitz II or higher atrioventricular nodal block), prolonged heart rate-corrected QT interval (longer than 470 milliseconds), or history of acute myocardial infarction. (The QT interval is the time between the start of the Q wave and the end of the T wave in the cardiac electrical cycle)
- Concomitant disease(s) that could prolong QT such as autonomic neuropathy (caused by diabetes or Parkinson's disease), human immunodeficiency virus (HIV), cirrhosis, uncontrolled hypothyroidism, or cardiac failure.
- Presence of active or suspected acute or chronic uncontrolled infection or history of immunocompromise, including a positive HIV test result.

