- Any severe and/or uncontrolled medical conditions or other conditions that could affect patient participation in the study such as severely impaired lung function, any active (acute or chronic) or uncontrolled infection/disorders, and nonmalignant medical illnesses that are uncontrolled or whose control may be jeopardized by the study therapy.

- Known or suspected allergy or hypersensitivity to any component of nivolumab or its analogues or any component of the proposed regimen (gene vector/Valacyclovir).
- Inability to swallow food or any condition of the upper gastrointestinal tract that precludes administration of oral medications (Valacyclovir). Any active malignancy except for non-melanoma skin cancer or in situ cervical cancer or treated cancer from which the patient has been continuously disease free for more than 5 years.
- Pregnant or breastfeeding women or women/men able to conceive and unwilling to practice an effective method of birth control. WOCBP must have a negative serum pregnancy test within 7 days prior to the administration of the first study treatment.
- Unwilling or unable to comply with the study protocol.

9. Treatment materials

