Investigations	Alkaline phosphatase increase (14-22%), ALT increase (12-16%), AST increase (16-28%), Total bilirubin increase (3-19%), Creatinine increase (13-22%), Weight decrease (13%, severe 1%).
Metabolism and nutrition	Decreased appetite (35%, severe 3%).
Musculoskeletal and connective tissue	Arthralgia (13%), Musculoskeletal pain (36%, severe 6%).
Respiratory, thoracic, and mediastinal	Cough (17%).
Skin and subcutaneous tissue	Pruritus (19%), Rash (21%, severe <1%).

Clinically significant immune-mediated adverse reactions can occur, including pneumonitis, colitis, hepatitis, nephritis, hypothyroidism, and hyperthyroidism. Immune reactions may be delayed or occur after nivolumab discontinuation. Based on the type and severity of the reaction, management may include withholding or discontinuing nivolumab, administering HD corticosteroids, and if appropriate, initiating hormone replacement therapy. Following resolution of the reaction to grade 1 or less, corticosteroids should be tapered over at least one month. Nivolumab should not be resumed while the patient is receiving immunosuppressive doses of corticosteroids or other immunosuppressive therapy. Restarting nivolumab may be considered following completion of corticosteroid taper. Permanent discontinuation of nivolumab is usually recommended following grade 3 or 4 immune-mediated reactions.

Supply and storage:

Injection: Bristol-Myers Squibb Company supplies nivolumab as 40 mg and 100 mg ready-to-use, single-use (preservative-free) vials in a concentration of 10 mg/mL. Refrigerate and store in original packaging to protect from light. Do not freeze or shake.¹⁸⁹

Solution and compatibility:

- Nivolumab should be clear and colorless to pale-yellow in color. Discard if cloudy or discolored.
- Nivolumab can be infused undiluted (10 mg/mL) or diluted with normal saline or 5% dextrose in water (to 0.35 mg/mL or greater).

Parenteral administration:

Intermittent infusion over 60 minutes.

Dosage guidelines:

The ENSIGN protocol's guidelines for dosing also include consideration of ANC. Dosage may be reduced, delayed, or discontinued in patients with bone marrow depression due to cytotoxic therapy/RT or other toxicities. (See Section 6 for management of immune-mediated complications of nivolumab)

Table 7. Nivolumab adult dosing

Route	Cycle Length:	Dose
IV	4 weeks	480 mg IV for one dose on day 1 (Total dose per cycle, 480 mg)

Table 7

10. Prohibited concomitant therapy

Antineoplastic therapies

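### Section 8.2 does not name the autoimmune, symptomatic interstitial lung disease and immunosuppression exclusions of the cited NSCLC nivolumab trials, and no entry criterion covers an earlier severe immune event or a running steroid taper

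*Combined protocol and SAP*

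**What the plan says.** **Source trials (Section 1.1).** For the phase III squamous NSCLC trial against docetaxel, and again for the single-arm squamous trial, the protocol reports: "Patients with autoimmune disease, symptomatic interstitial lung disease, or untreated brain metastasis were excluded". For the phase III non-squamous trial it reports: "The trial excluded patients with autoimmune disease, medical conditions requiring systemic immunosuppression, symptomatic interstitial lung disease, or untreated brain metastasis". It presents these trials as the evidence for nivolumab in metastatic NSCLC.

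**Entry criteria (Sections 7, 8.1 and 8.2).** Two steroid uses are excluded by name: "Patients requiring oral prednisone for emphysema management (NSCLC cohort only" and "brain or leptomeningeal metastases requiring continued glucocorticoid treatment". Broader clauses include "history of immunocompromise, including a positive HIV test result", "severely impaired lung function" (one example within a general exclusion of serious or uncontrolled conditions), non-malignant illnesses that study treatment might destabilise, and the treating physician's view that a finding puts the patient at risk. NSCLC patients must have progressed after a single-agent immunotherapy. The limits on that earlier treatment are a 2-week washout and adequate recovery from its acute toxicity.

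**On-study rules.** Section 6: "Permanently discontinue nivolumab for severe (Grade 3) or life-threatening (Grade 4) immune-mediated complications". Section 12.4 lists the same events as a reason for withdrawal. Section 9.4 is softer, since it says permanent discontinuation is usually recommended. It adds that immune reactions may be delayed, that corticosteroids are tapered over at least one month once the reaction has fallen to grade 1 or less, and: "Nivolumab should not be resumed while the patient is receiving immunosuppressive doses of corticosteroids or other immunosuppressive therapy".

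**The concern.** The protocol describes the patients in whom nivolumab was tested in NSCLC and then writes entry criteria that do not name three of the reported exclusions. Brain metastasis is the one reported exclusion with a clear named counterpart in Section 8.2.

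In the NSCLC cohort, prior immunotherapy is a condition of entry, so some candidates may have had a severe immune-mediated event on it. The protocol treats that event as decisive when it happens on study and does not mention it at entry.

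What is at stake is mainly patient safety. Section 1.1 calls pneumonitis the most important adverse effect in the phase 1 nivolumab trial, with 3 deaths, and Section 9.3 lists pneumonitis among the side effects of SBRT. A Grade 3 or higher event in such a patient would also count in the Section 15.1 run-in, which opens a cohort fully only if no more than 1 of 6 patients has toxicity.

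**Working it through.** **1. The plan's own figures.** The only computed figures nearby are the powers in Section 15.1, and both reproduce with an exact one-sample binomial.
- NSCLC, n = 16, success at 3 or more responses: power = P(X ≥ 3 | 0.25) = 0.8029 (stated 80.3%); alpha = P(X ≥ 3 | 0.03) = 0.0113.
- Uveal melanoma, n = 9, success at 2 or more responses: power = 1 − 0.7^9 − 9 × 0.3 × 0.7^8 = 0.8040 (stated 80.4%); alpha = P(X ≥ 2 | 0.03) = 0.0282.

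These depend only on n, the cut-off and the two response rates. Adding exclusions leaves them unchanged, so the rest of the check is a comparison of text.

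**2. Side by side.**

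| Item | Reported elsewhere in the protocol | Named in 8.1 or 8.2? | Nearest clause |
|---|---|---|---|
| Autoimmune disease | Excluded in all three NSCLC trials (1.1) | No | Illnesses that study treatment might destabilise; physician opinion |
| Symptomatic interstitial lung disease | Excluded in all three NSCLC trials (1.1) | No | Severely impaired lung function; physician opinion |
| Conditions requiring systemic immunosuppression | Excluded in the non-squamous trial (1.1) | No | History of immunocompromise; the two steroid exclusions |
| Earlier Grade 3-4 immune-mediated event | Discontinuation or withdrawal on study (6, 12.4); discontinuation usually recommended (9.4) | No | Recovery from acute toxicity; 2-week washout |

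Section 10 restricts only other anticancer treatment, so it does not cover steroids or other immunosuppressants.

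**3. Does the immunocompromise clause cover steroids?** Probably not by intent. If it did, the two specific steroid exclusions would be redundant. As written, a uveal melanoma patient taking prednisone for any reason other than brain or leptomeningeal disease meets no named steroid exclusion. The same holds for an NSCLC patient whose reason is neither that nor emphysema.

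**4. Washout against taper.** The washout is 14 days before study treatment. The shortest taper in Section 9.4 is one month, taken here as 28 to 31 days.
- Suppose the taper began on the day of the last immunotherapy dose, which is the earliest case. At day 0, 28 − 14 = 14 to 31 − 14 = 17 days of it would remain. It would overlap the vector injection (day 0), SBRT (days 2 to 14) and valacyclovir (days 1 to 15).
- First nivolumab is on day 17, so 14 + 17 = 31 days after the last earlier dose. A minimal taper would just have ended.
- A taper starts only after the reaction has resolved to grade 1 or less, reactions may be delayed, and one month is a minimum. A later or longer taper can still be running at the first nivolumab dose, and no named criterion would detect it.

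The protocol does not say what counts as an immunosuppressive dose.

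**The case against.** The strongest reply is that the general clauses already do the work. Excluding illnesses that study treatment might destabilise readily reaches autoimmune disease when that treatment is an anti-PD-1 antibody. The recovery criterion is a partial safeguard after earlier immunotherapy, and the physician may exclude anyone judged at risk. This stands in part: many such patients would probably be kept out. But the outcome rests on judgement, symptomatic interstitial lung disease need not mean severe impairment, and Section 8.2 elsewhere names its conditions in detail.

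Three further points stand and limit the concern.
- The sources excluded only symptomatic interstitial lung disease, and only one is reported as excluding systemic immunosuppression. The squamous trials allowed patients with treated brain metastases on less than 10 mg prednisone equivalents daily, so some steroid use at entry agrees with the sources.
- Sections 6, 9.4 and 12.4 govern conduct on study and are not entry rules. Their silence about earlier events is a gap to reconcile. It is not a formal contradiction, and it does not follow that the Section 6 stopping rule should become an eligibility rule.
- The reported exclusions come from lung trials. Section 1.1 describes the melanoma trials without them, and uveal melanoma patients here are immunotherapy naïve. Extending the list to that cohort has no source in the documents.

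A reader might also infer that the run-in gate is likely to fail. The documents do not support this. The Grade 3-4 rates of 17% and 22% in Section 1.1 are whole-trial rates, while the run-in ends after nivolumab cycle 1, and the share of affected patients is unknown. If that share were 10% (an assumption) and every such patient had toxicity, the overall rate could rise at most from 17% to 0.9 × 17% + 10% = 25.3%, or from 22% to 0.9 × 22% + 10% = 29.8%. That is a ceiling and not an estimate.

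**Conclusion.** The concern holds as a gap in the entry criteria. Three conditions reported as exclusions in the cited NSCLC trials, and one event that ends nivolumab on study, are not named at entry. Only two steroid uses are excluded by name. The general clauses reduce the gap without closing it, and the 2-week washout sits badly with tapers of at least one month.

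No numerical effect on safety or response can be derived, because the documents give neither the frequency of these patients nor their outcomes. Two further inferences should be resisted.
- That immunosuppressed patients would lower the ORR: this is plausible, but nothing in the documents quantifies it.
- That the quoted toxicity figures do not apply to such patients: the eligibility behind the 22% rate is not stated, so the most one can say is that the figures are not shown to apply.

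The conclusion assumes that no unseen study manual or screening form already lists these conditions.

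**What to change.** Amend Section 8.2 as follows.

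1. For the NSCLC cohort, name autoimmune disease, symptomatic interstitial lung disease and conditions requiring systemic immunosuppression as exclusions, or state why the source-trial exclusions do not apply here.
2. State whether the same items apply to the uveal melanoma cohort, and why.
3. Reconcile the entry criteria on earlier immune-mediated events and on current corticosteroid use with Sections 6, 9.4 and 12.4, including the difference in firmness between Sections 6 and 9.4. The sponsor's clinicians decide the rule.

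The cost is one eligibility amendment, a few more screen failures and slightly slower accrual. Sample sizes and the Section 15.1 power figures stay as they are.

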9.1 ADV/HSV-tk

Replication-defective recombinant adenovirus vector.

The viral vector proposed here has been used for multiple ongoing Investigational New Drugs (INDs), including BB-IND 6371, 6636, 6599, and 7311. The vector is a first-generation adenoviral construct based on an adenovirus serotype-5 backbone.

The therapeutic potential of HSV-tk gene therapy is greatly enhanced by a “bystander effect” in which cytotoxicity is conferred to non-transduced neighboring cells. *In vivo* bystander effects are likely due to a combination of host immunological responses and to gap junction-mediated transport of phosphorylated prodrug metabolites to surrounding cells.

Many laboratories have shown the *in vitro* susceptibility of mouse and human prostate cancer cells to HSV-tk/prodrug treatment. Our group has evaluated the effects of ADV-tk + GCV on *in vivo* tumor growth and survival in mouse prostate cancer models.⁸⁰ An adenoviral vector carrying the HSV-tk gene under the control of the Rous sarcoma virus promoter was administered by direct intratumoral injection.⁸⁰⁻⁸² Tumor growth was significantly delayed in the ADV-tk + GCV group compared with the control groups (ADV-tk + saline and ADV-β-galactosidase [control vector] + saline or GCV).⁸⁰ Tumor volume in the ADV-tk + GCV-treated group was 16% of that in the combined control groups. However, with longer follow-up, ADV-tk + GCV-treated tumors began to grow at a rate similar to control tumors. Mean survival was 14.2 ± 0.6 days for the combined control groups and 21.2 ± 1.3 days for the treatment group ($P < 0.001$ by Mantel-Cox log-rank analysis). Animal studies have also shown that ADV-tk treatment can protect against metastases. In an orthotopic model, the spontaneous metastasis rate was significantly lower for the ADV-tk + GCV treatment group compared with the pooled control groups (12.5% [2/16] vs. 71.4% [10/14]; $P = 0.0032$ by Fisher's Exact test).⁸³ Similar results were obtained in experimental metastasis models (i.e., tail vein injection of tumor cells). HSV-tk/GCV gene therapy in combination with radiation significantly prolonged survival compared with either therapy alone and sham treatment (22.9 ± 1.34 days vs. 16.9 ± 0.84 days and 11.3 ± 0.77 days, respectively; $P < 0.001$ by log-rank and Wilcoxon tests).⁸³

Based on extensive efficacy and toxicity studies in mice, cotton rats and non-human primates^{81, 84} our group designed a dose escalation phase I clinical study to evaluate the potential toxicity of ADV/HSV-tk in humans (Regulatory Affairs Certification [RAC] protocol # 9601-144). The study was evaluated and approved by the local (institutional review board [IRB] and institutional biosafety committee) and national (RAC and FDA) regulatory bodies. Subjects included men with locally recurrent prostate cancer after RT. Vector particles (2×10^9 to 2×10^{12}) were administered in a single intratumoral injection guided by ultrasound imaging. Three patients achieved partial responses, and only occasional transient toxicities were observed (Phase I Study of Adenoviral Vector Delivery of the HSV-tk Gene and the Intravenous Administration of Ganciclovir in Men with Local Recurrence of Prostate Cancer after Radiation Therapy, National Institutes of Health-Office of Recombinant DNA Activities # 9601-144).⁸⁵

Based on our favorable preclinical and clinical trial data, a phase I-II study was designed to analyze the efficacy and toxicity of HSV-tk gene therapy in combination with RT in prostate cancer patients.⁸⁶ In this study, intravenous GCV was replaced with valacyclovir (Valtrex, Glaxo Wellcome), an orally administered medication that is rapidly and almost completely metabolized in the liver to acyclovir. The trial consisted of 3 treatment arms: Arm A, low-risk patients treated with HSV-tk/valacyclovir + RT; Arm B, high-risk patients treated with the same regimen as Arm A with the addition of hormonal therapy; and Arm C, patients with stage D1 (positive pelvic lymph nodes) who received the same regimen as Arm B with the addition of 45 Gy to the pelvic lymphatics. Fifty-nine patients (29 in Arm A, 26 in Arm B, and 4 in Arm C) completed the trial. The median age was 68 years (range: 39–85 years). The median follow-up for the entire group was 13.5 months (range: 1.4–27.8 months). Only Arm A patients were observed to have an increase in prostate specific antigen (PSA) on day 14, which then declined appropriately. All patients in Arm A (median follow-up: 13.4 months) and Arm B (median follow-up: 13.9 months) had biochemical control at last follow-up. Three patients in Arm C (with pretreatment PSA of 335, 19.6, and 2.5 ng/mL and a combined Gleason score of 8, 9, and 9 involving all biopsy cores) had biochemical failure at 3, 3, and 7.7 months. Two patients had distant failure in bone and 1 patient in the para-aortic lymph nodes outside the radiation portal. Six to twelve prostate biopsies performed in these 3 patients revealed no evidence of residual carcinoma. In Arm A, biopsy showed no evidence of carcinoma in 66.7% (18/27), 92.3% (24/26), 91.7% (11/12), 100% (8/8), and 100% (6/6) of patients at 6 weeks, 4 months, 12 months, 18 months, and 24 months after treatment, respectively. In Arm B, biopsy showed no evidence of carcinoma in 96% (24/25), 90.5% (19/21), 100% (14/14), 100% (7/7), and 100% (2/2) of patients at 6 weeks, 4 months, 12 months, 18 months, and 24 months after treatment, respectively. This was the first reported trial of its kind in the field of prostate cancer that aimed to expand the therapeutic index of RT by combining it with in situ gene therapy.⁸⁷

Dosage:

ADV/HSV-tk will be administered intratumorally at 5×10^{11} virus particles on day 0. This dose is based on the toxicity results from the phase I/II study of ADV-tk gene therapy in combination with chemoradiation in patients with pancreatic adenocarcinoma.⁷⁷ If toxicity occurs, ADV/HSV-tk dose will be reduced to 5×10^9 vector particles per injection. If toxicity occurs with this dose modification, the dose will be further reduced to 5×10^6 virus particles per injection.

Delivery:

For the NSCLC cohort, the tumor will be identified by PET/CT by the radiation oncologist. The procedure will be managed under endoscopic ultrasound (EUS) guidance. In rare cases where the tumor cannot be accessed by EUS, a CT-guided injection will be performed. For the uveal melanoma cohort, the procedure will be managed under ultrasound or CT guidance. EUS will be performed with the patient under sedation. Patients will be monitored until the sedation has worn off. For CT-guided injections, local anesthesia will be used and patients will be monitored for several hours after the procedure.

Warnings and precautions:

Significant toxicity has not been observed with the administration of ADV/HSV-tk gene therapy alone or in combination with RT or chemotherapy in previous clinical trials.^{85, 88-90} Fever may occur due to the local inflammatory and immune response to ADV/HSV-tk, which will be treated with acetaminophen as necessary. If local inflammation is extensive or infection develops, Valacyclovir will be stopped and antibiotics and/or anti-inflammatory therapy will be given as appropriate. Other potential side effects of ADV/HSV-tk gene therapy include increased creatinine, increased liver enzymes (ALT, AST, alkaline phosphatase, and gamma-glutamyl transferase), increased bilirubin, cellulitis, and thrombocytopenia.

